7.1.4 Computed Tomography

CT scan with contrast will be performed to assess all known diseases in patients with solid tumors. CT scans must encompass neck, chest, abdomen, and pelvis and include oral or intravenous contrast. MRI may be used in place of CT in clinical scenarios where anatomical location of an evaluable lesion (such as soft tissue) precludes accurate measurement by CT. The CT scan will be used for disease assessment by the investigator at each study center. For patients who discontinue early, a CT scan will be performed at the end of study visit if the previous scan was more than 3 months ago. Note: CT scans do not apply to patients with AML.

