3.2 Secondary Endpoints

Blood sample collection:

Cycle 1 Day 1: pre-dose, post dose 5, 15, 30 minutes, 1, 2, 4, 6, 8, 12, 24, and 48 hours and on Day 8 prior to that days dose (if applicable)

PK for single dose profile:

August 21, 2019 Confidential 30 / 74

AUC from zero to the last measurable concentration (AUC_{0-last}), AUC from 0 to 24 hours (AUC₀₋₂₄), AUC from zero to infinity (AUC_{0- ∞}), C_{max}, time to maximum observed plasma concentration (t_{max}), t_{1/2}, CL, apparent volume of distribution (Vd), and Linear Index (LI).

Endpoints for anti-tumor activity evaluation

Anti-tumor activity will be evaluated by investigators according to Response Evaluation Criteria in Solid Tumors (RECIST) v1.1 (solid tumor), performance status, and Computed Tomography (CT)/ Magnetic Resonance Imaging (MRI) image at designated time point and time of event. Imaging for disease assessment will be performed every 6 weeks to summarize CR, partial response (PR), stable disease (SD), progression-free survival (PFS), and duration of response for patients with solid tumors.

In patients with AML, response will be evaluated according to the AML response criteria [5]. Bone marrow assessments will be performed at Screening, the end of every other cycle, and at the end of the study or at time of relapse.

Based on the patient's clinical condition, complete blood counts or bone marrow assessments may occur more frequently based on Investigator's judgment.

4 Investigational Plan

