4.1 Summary of Study Design

This is a phase 1, first-in-human, open-label, multi-center, single-arm, dose escalation clinical study in patients with histologically or cytologically confirmed advanced solid tumors or relapsed/refractory AML, who cannot tolerate or do not respond to standard systemic therapy.

Patients will be screened for eligibility for up to 21 days prior to entry into the study. The starting dose will be 2.5 mg/day on the assigned days. Dose escalation will use the traditional 3+3 design and follow a modified Fibonacci sequence until MTD is reached. Increments of 33% in the dose of FN-1501 will be undertaken after reaching 30 mg/day. Eligible patients will receive a single intravenous infusion of study drug on Days 1, 3, 5, 8, 10, and 12 of a 21-day cycle.

The DLT assessment period is 21 days from the first dose of FN-1501. Evaluation of a cohort of at least three (3) patients completing DLT assessment at any given dose level is required prior to determining the next dose level and dose regimen for the subsequent cohort.

August 21, 2019 Confidential 31 / 74

The highest dose under which one or no case of DLT is observed will be considered as MTD. If DLT cannot be observed, RP2D will be determined based on safety, preliminary anti-tumor activities and PK data.

Approximately thirty-three patients are expected to be enrolled.

After the first patient in the cohort receives the Cycle 1, Day 1 dose, subsequent patients in that cohort will not be dosed until the first patient has been evaluated for at least 48 hours to exclude unexpected acute toxicity. The continuous safety evaluation will be performed by investigators, the medical monitor, and the sponsor. A Safety Monitoring Committee (SMC) will determine dose levels to be administered and dose regimen during dose escalation based on the data available from the previous dose levels. If an MTD is not identified due to paucity of DLTs, the RP2D will be determined based on PKs, safety, tolerability, and preliminary efficacy.

If a patient wishes to continuously receive study treatment on completion of Cycle 1, the patient can continue study treatment in 21-day Cycle 2 and subsequent cycles (same as Cycle 2, all of 21 days' duration), defined as administration of 3 times per week for 2 weeks followed by 1 week rest, at the discretion of the investigator.

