4.1.3 Study Procedures

Study procedures are listed and described in Table 2. Detailed descriptions of the time points for PK sampling, ECG, and vital signs evaluations in the first week of Cycle 1 is included in Table 3.

August 21, 2019 Confidential 35 / 74

Table 2: Study Assessment and Procedure Schedule

Assessment	Screen period		Cycle 1 (21 days)						Subseq	uent 21 days)	Follow-up/ End of Study
Day of Cycle	-21 to	1 ¹	2	3	5	8	10	12	1 ² (±3)	8 (±3)	30 to 35 days post last dose
Inform consent	X										
Review eligibility	X										
Demographic data	X										
Medical history/ baseline conditions	X										
Disease assessment Solid Tumors ³	X		Every 6 weeks \pm 5 days and as detailed in the footnote								
Disease Assessment AML ³	X		Every 6 weeks \pm 5 days and as detailed in the footnote								
Vital signs	X	X^4	X	X ⁴	X ⁴	X^4	X^4	X^4	X^4	X ⁴	X
Weight	X	X^4	X	X ⁴	X ⁴	X^4	X^4	X ⁴	X^4	X ⁴	X
Physical exam ⁵	X	X^4	X	X ⁴	X^4	X^4	X^4	X ⁴	X ⁴	X ⁴	X
ECOG performance review	X	X ⁴				X ⁴			X^4		X
12-lead ECG ⁶	X	X							X		X
Concomitant medications review	X	X				X			X		X
CT or MRI (solid tumor only)	X ⁷	Every 6 weeks ± 5 days									
Pregnancy test ⁸	X	X							X		
Hematology ⁹	X	X ⁴				X^4			X ⁴	X^4	X
Blood chemistry + amylase and lipase tests ⁹	X	X^4				X ⁴			X ⁴	X^4	X

August 21, 2019 Confidential 36 / 74

Assessment	Screen period		Cycle 1 (21 days)						Subsequent cycles (21 days)		Follow-up/ End of Study
Day of Cycle	-21 to	1 ¹	2	3	5	8	10	12	1 ² (±3)	8 (±3)	30 to 35 days post last dose
Bone Marrow Biopsy for patients with AML ¹⁰	X			Every	6 wee	eks ± :	5 days	and as	detailed i	n the footn	ote
Coagulation test ⁹	X										X
Urinalysis ¹¹	X								X		X
Adverse event	X						Хс	ontinuo	ous		
PK blood sample		X	X	X ¹²					X ¹²		
Study drug ¹³ administration		X		X	X	X	X	X	X	X	

Abbreviations: AML = Acute Myeloid Leukemia; BMI = Body Mass Index; CT = computed tomography; ECOG = Eastern Cooperative Oncology Group; MRI = magnetic resonance imaging; PK = pharmacokinetic

- 1. On Day 1 of Cycle 1, patients may need to stay at the clinical research unit overnight to complete PK sampling, safety observation and assessments.
- 2. For DLT cycle, patients will return for the end of the DLT assessment period (21 days from first dose of FN-1501) assessments on Day 1 of Cycle 2 (± 3 days). If additional cycles are planned, patients will start Day 1 dosing of next cycle after the assessments. For the last cycle, patients will return for the assessments.

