- 3. Disease assessment every 6 weeks to coincide with every other cycle. Refer to Section 7.4 for details.
- 4. These assessments should be conducted, and the results should be available before study drug administration in each cycle. If assessments are conducted within 3 days prior to Day 1 of the cycle, the data can be recorded as Day 1 data of the cycle. See Table 3 for details. Height to be measured at Screening for BMI calculation.
- 5. A full physical exam will be conducted at screening, on Day 1 of each cycle and at follow-up. A full physical exam includes assessments of cardiovascular, respiratory, abdominal and neurological systems as well as lymph nodes/spleen, skin, oropharynx and extremities. Refer to Section 7.1.2 for details.

August 21, 2019 Confidential 37 / 74

6. ECGs to be performed prior to that days dose (if applicable) and after the patient has been supine for at least 10 minutes and should be performed with the patient in the same physical position for the duration of the test. ECG at Screening: performed in triplicate (5-10 min between readings). ECG at Day 1 of Cycle 1: performed in triplicate (5-10 min between readings) at the days indicated in Table 2 and time points and time windows detailed in Table 3. Cycle 2 Day 1: Perform in triplicate (5-10 min between readings) only if patient has a significant QTc prolongation, that is, a) > 500 msec; or b) increased by ≥ 60 msec over baseline; and/or c) decreased by 50 msec below pre-dose recording. If prolongation of QT or QT interval corrected for heart rate (QTc) is noted during the first 2 weeks, triplicate 12 lead ECGs will be conducted weekly during Cycle 2, and then once every 3 weeks before administration and 5-15 minutes after administration on Day 1 of every cycle from Cycle 3 onwards, until discontinuation of FN-1501 treatment. Refer to Section 7.1.3 for details on significant QTc prolongation.

- 7. Data obtained up to 42 days prior to Day 1 is acceptable.
- 8. Only in women of childbearing potential and additionally at the investigator's discretion.
- 9. In the event of neutropenia, thrombocytopenia, or \geq Grade 3 clinical chemistry toxicity, these assessments will be conducted as frequent as the investigator feels necessary until toxicity is resolved (\leq Grade 2). Refer to Table 6 for details on laboratory assessments.

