4.2.4.2 Patient Discontinuation

A patient must be discontinued if any one or more of the conditions occur: 1) DLT occurs and the toxicity has not improved to Grade 1, Grade 0 or baseline within 14 days of onset; 2) occurrence of other toxicities that makes continuation of study treatment intolerable; 3) a third dose-reduction is required; 4) treatment delay is more than 4 weeks, unless resuming treatment is regarded beneficial to the patient by the investigator and agreed by Sponsor's medical monitor; 5) in the opinion of the investigator, continuous treatment is not beneficial to the patient.

A patient may voluntarily discontinue participation from this study at any time. If a patient is discontinued from participation in the study for any reason, the investigator must make every effort to perform the following evaluations 30 to 35 days from the last dose of FN-1501: physical examination, vital signs, ECG, laboratory tests (hematology, chemistry, coagulation, and urinalysis), and AE assessment. These data will be recorded as they comprise an essential evaluation that should be done prior to

August 21, 2019 Confidential 43 / 74

discharging any patient from the study. If a patient is discontinued from the study at any time due to an AE (as defined in Section 9.1), the procedures stated in Section 9.7 must be followed.

The reason for discontinuation will be recorded in the electronic case report form (eCRF). These reasons may include:

- Withdrawal of consent by the patient
- Discontinuation of FN-1501 by the sponsor
- Pregnancy
- Any significant AE that compromises the patient's ability to participate in the study
- The investigator or sponsor determines it is in the best interest of the patient
- Progression of disease at any time during the study
- Need for prohibited medication
- Lack of compliance with the study and/or study procedures (e.g., administration instructions, study visits)
- Significant deviation from the protocol without the consent of the sponsor

Premature discontinuation of FN-1501 occurs when a patient is discontinued for reasons other than unacceptable toxicity during DLT evaluation cycle. Prematurely discontinued patients will be considered for replacement after due consideration from sponsor and SMC.

5 Study Treatments

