5.2.1 Dose Delays and Modifications

Interruption/reduction of dosing for AEs may take place any time during the study. Below are general guidelines for dose delays and modifications for FN-1501 related toxicities.

Dose Delays

Treatment with FN-1501 should be withheld from a patient who experiences an AE of Grade 3 or higher until the toxicity resolves to Grade 1, Grade 0 or baseline. Dosing with FN-1501 may be resumed following resolution of toxicity at the next lower dose level. The resumed dosing will be given at the next regularly scheduled time point. If the AE is clearly not associated with the study treatment, the dosing may be resumed at the original dose level, after discussion with the sponsor's medical monitor.

If a patient requires a treatment interruption of more than 4 weeks for any reason, the patient should be withdrawn from the study treatment, unless resuming the treatment is regarded beneficial to the patient by the investigator and agreed upon by the sponsor's medical monitor.

Dose Modifications

Dose reductions are allowed if patients resume study treatment after dose interruption for toxicity. A maximum of two dose reductions are permitted. If further dose reduction is needed, the patient should be withdrawn from study treatment.

A patient may switch to a higher dose at the discretion of the investigator, if 1) the safety of the higher dose level has been fully evaluated and determined not to exceed MTD; and 2) the patient has been treated at the current dose level for at least 2 cycles without experiencing a clinically significant treatment-emergent AE. However, if Grade 3 or higher toxicity occurs or continues after permitted dose increase or reduction, then the patient should be withdrawn from study treatment.

Any resumed or modified dose will start as a new cycle.

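### Is the 3-month trigger for the end-of-study CT too long for a trial that images every 6 weeks?

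*Protocol*

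**What the plan says.** Protocol Section 7.1.4 holds the only express exit-imaging rule for solid tumours: when a patient discontinues early, "a CT scan will be performed at the end of study visit if the previous scan was more than 3 months ago". Section 3.2 sets the regular schedule: "Imaging for disease assessment will be performed every 6 weeks". Table 2 (Section 4.1.3) gives this a window of 5 days either side, and its footnote 3 ties disease assessment to every other 21-day cycle. For the baseline scan, footnote 7 states: "Data obtained up to 42 days prior to Day 1 is acceptable". The follow-up column of Table 2 places the end-of-study visit at "30 to 35 days post last dose".

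Section 4.2.4.2 lists what must be attempted when any patient is discontinued: "physical examination, vital signs, ECG, laboratory tests (hematology, chemistry, coagulation, and urinalysis), and AE assessment". Imaging is not on that list. Sections 3.2 and 7.4 also provide for tumour evaluation at the time of an event, a term that they do not define.

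**The concern.** A trigger of 3 months beside a 6-week schedule looks like a rule that seldom operates. A patient who stops for toxicity or withdraws consent between scans could leave with no tumour assessment near exit, and one who stops in Cycle 1 could have none after baseline.

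Response, PFS and duration of response are secondary endpoints. Section 4.1 adds that, if too few DLTs occur to identify an MTD, "the RP2D will be determined based on PKs, safety, tolerability, and preliminary efficacy". Cohorts hold about three to six patients, so one patient classed as not evaluable is a visible share of a dose level's response data. A scan that was never taken cannot be recovered at analysis.

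**Working it through.** The plan states no figure to reproduce, so the check is a day count.

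**Inputs**
- Trigger: more than 3 months (Section 7.1.4). Days are not defined. Three calendar months are 89 to 92 days (assumption); read as 12 weeks, 84 days.
- On-study scans: every 42 days, window ±5 days (Table 2).
- Oldest permitted baseline scan: 42 days before Day 1 (Table 2, footnote 7). A scan 21 days before Day 1, the start of the screening window, serves as comparison.
- End-of-study visit: 30 to 35 days after the last dose (Table 2).
- Dosing on Days 1, 3, 5, 8, 10 and 12 (Section 4.1). In days after the first dose: Cycle 1 Day 12 = 11; Cycle 2 Day 1 = 21; Cycle 2 Day 12 = 32; Cycle 3 Day 1 = 42; Cycle 3 Day 5 = 46; Cycle 4 Day 12 = 74.

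**Formula.** Age of last scan at the visit = days from last scan to last dose + 30 to 35. This assumes no imaging between the last dose and the visit.

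| Situation | Sum | Age (days) | Beyond 3 months? |
|---|---|---|---|
| Cycle 1 stop, Day -42 baseline | 42 + 11 + 35 | at most 88 | no |
| Cycle 1 stop, Day -21 baseline | 21 + 11 + 35 | at most 67 | no |
| Between on-study scans, full windows | 42 + 5 + 5 + 35 | at most 87 | no |
| Between on-study scans, exactly on time | (74 - 42) + 35 | at most 67 | no |
| Cycle 2 stop, Day -21 baseline | 21 + 21 + 30 to 21 + 32 + 35 | 72 to 88 | no |
| Cycle 2 stop, Day -42 baseline | 42 + 21 + 30 to 42 + 32 + 35 | 93 to 109 | yes |
| Early Cycle 3 stop before a late first scan, Day -21 baseline | 21 + 42 + 30 to 21 + 46 + 35 | 93 to 102 | yes |
| Same, Day -42 baseline | 42 + 42 + 30 to 42 + 46 + 35 | 114 to 123 | yes |
| 4-week interruption, scans tied to cycles | 32 + 28 + 35 | 95 | yes |
| First on-study scan missed, last dose Cycle 4 Day 12, baseline at first dose | 74 + 30 to 74 + 35 | 104 to 109 | yes |

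On the exact dosing grid the between-scan maximum is 86 rather than 87: a scan 5 days early, then a last dose 51 days later on Day 5 of the cycle in which the next scan is due, gives 51 + 35.

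**If 6-weekly imaging continues to the visit.** The first on-study scan is due 42 ± 5 = 37 to 47 days after the first dose. A patient whose last dose is Cycle 1 Day 8, 10 or 12 has the visit between 7 + 30 = 37 and 11 + 35 = 46 days, inside that window. Scan and visit then coincide without any exit rule.

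**What a 6-week trigger would do.** It fires when the last dose comes more than 42 - 35 = 7 to 42 - 30 = 12 days after the last scan. Between on-study scans, those are the patients whose next 6-weekly scan falls due by the visit anyway. It would add something mainly for a stop in the first days of Cycle 1 with an older baseline scan.

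**The case for a change.** The strongest case for a change is that the two groups the rule misses are ordinary ones: patients on schedule who leave in Cycle 1 or between scans. AML patients have a marrow assessment at the end of the study with no condition on the age of the last one, and no reason is given for treating solid tumours differently. The Amendment 3 rationale reports no DLT in nine evaluable patients, so choosing the RP2D partly on preliminary efficacy is a realistic prospect. That amendment also moved solid-tumour assessment to 6-weekly, so the 3-month figure may be a carry-over, although that is inference.

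The day counts stand, as does the absence of imaging from Section 4.2.4.2. The rest is weaker:
- Sections 4.2.4.2 and 7.1.4 do not conflict. One lists evaluations for every discontinued patient; the other adds a conditional CT for solid tumours.
- The gap exists only if imaging stops with the last dose. The CT row of Table 2 has one 6-weekly entry after screening, and the extracted table does not show whether it spans the follow-up column. Footnote 3 favours a cycle-bound reading but does not settle it.
- Section 10.2.3 replaces, where possible, patients who withdraw before the end of the DLT period for reasons other than DLT. This softens the Cycle 1 loss, though not for a patient who stops because of a DLT.
- A scan 30 to 35 days after the last dose is not an assessment at treatment exit. Section 6.2 bars other anti-cancer therapy only during study treatment, so new therapy may already have begun.

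**Conclusion.** No change is called for. On the reading least favourable to the plan, the rule misses on-schedule stops in Cycle 1 (at most 88 days) and between on-study scans (at most 86 to 87 days), by a margin of a few days against 89 to 92. Read as 12 weeks, the 85-to-88-day extremes would trigger it. It does fire in the longer gaps, including some on-schedule patients with no scan since baseline, which is what a backstop is for.

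Shortening the trigger gains little on either reading of Table 2. If 6-weekly imaging runs to the visit, that schedule already supplies nearly all the scans in question. If it does not, the price is a further contrast CT from neck to pelvis for most early leavers without documented progression, at a time when the result may reflect later treatment. The data served are descriptive: Section 7.4 says efficacy is not a primary objective, and Section 10.5 already provides a not-evaluable category. The effect on those summaries cannot be sized from the protocol, since it depends on how many patients stop this way and on censoring rules that belong to the SAP, which was not available here. Whether imaging continues after the last dose is a missing detail that the study team can settle operationally, not a fault in the design.

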7.1.5 Adverse Events

All AEs and SAEs, regardless of the relationship to the study drug, will be collected from consenting patients, starting from signed informed consent form until 30 days after their last dose of FN-1501, or until resolution of all study drug related AEs, whichever is longer.

7.2 Safety

Measurements used to evaluate safety will include vital signs, clinical laboratory tests, 12-lead ECG, and physical examinations. Throughout the study, the study center personnel will be monitoring AEs. AEs and toxicities will be graded according to NCI CTCAE, Version 4.03.

7.2.1 Pregnancy

7.2.2.1 Pregnancy Testing

A serum pregnancy test will be performed at screening and a urine pregnancy test at the time points specified in Table 2 in women of childbearing potential. Any female patient who is pregnant will not be eligible for the study.

August 21, 2019 Confidential 53 / 74

The results of pregnancy tests will be recorded in the database.

7.2.2.2 Time Period for Collecting Pregnancy Information

The time period for collecting information on whether a pregnancy occurs is from screening to the 30-day post-study follow-up/end of study visit. Information on pregnancies identified prior to the study drug administration does not need to be reported to the sponsor.

7.2.2.3 Action to be Taken if a Pregnancy Occurs

A patient who has a positive pregnancy test result at any time after the study drug administration will be immediately withdrawn from participation in the study. All post-study assessments will be collected at the time of discontinuation. The investigator, or his/her designee, will collect pregnancy information on any female patient or a female partner of a male patient who becomes pregnant while participating in this study.

The investigator, or his/her designee, will record pregnancy information on the appropriate form and submit it to the sponsor within 24 hours of learning of a patient's pregnancy. The patient will also be followed to determine the outcome of the pregnancy. Information on the status of the mother and child will be forwarded to the sponsor. Generally, follow-up will be no longer than 6 to 8 weeks following the estimated delivery date. Any premature termination of the pregnancy will be reported.

While pregnancy itself is not considered to be an AE or SAE, any pregnancy complication or elective termination of a pregnancy for medical reasons will be recorded as an SAE, as described in Section 9.6 and will be followed as described in Section 9.8.

A spontaneous abortion is always considered to be an SAE and will be reported. Furthermore, any SAE occurring because of a post-study pregnancy and which is considered reasonably related to the study drug by the investigator, will be reported to the sponsor as described in Section 9.8. While the investigator is not obligated to actively seek this information in former patients, he/she may learn of an SAE through spontaneous reporting.

